10.1.5 Oversight Committees

Safety reviews may be performed routinely by the local study site PIs and/or sponsor's staff in the course of the trial. Any questions pertaining to the reported clinical data will be submitted to the investigator for resolution. Each step of this process will be monitored through the implementation of individual passwords to maintain appropriate database access and to ensure database integrity.

10.1.6 Data Safety Monitoring Board

An independent committee (composed of three individuals) will be assembled to follow the study charter as proposed above.

10.1.7 Dissemination of Clinical Study Data

Study information and tabular study results will be posted on the US National Institutes of Health's website www.clinicaltrials.gov within one year of study completion.

10.1.8 Data Quality Assurance

All participant data relating to the study will be recorded on the electronic CRF unless transmitted to the sponsor or designee electronically (e.g., imaging). The investigator is responsible for verifying that data entries are accurate and correct signing the CRF. The investigator must maintain accurate documentation (source data) that supports the information entered in the CRF.

The investigator must permit study-related monitoring, audits, IRB review, and regulatory agency inspections and provide direct access to source data documents. The investigator agrees to allow the monitor(s) direct access to all relevant documents, and to allocate his/her time and the time of staff to discuss findings, corrective actions and any relevant issues. In addition to contacts during the study, the monitor may also contact the site prior to the start of the study to discuss the protocol and data collection procedures with site personnel.

Except for an emergency situation in which proper care for the protection, safety and well-being of the study participants requires medical treatment, the study will be conducted as described in the approved protocol, ICH GCP, SOPs and regulatory requirements. All medical treatments will be recorded. Any deviation(s) from the protocol will be recorded and presented in the final clinical study report.

The sponsor will determine the extent, nature, and frequency of on-site visits that are needed to ensure that the study is being conducted in accordance with the approved protocol (and any amendments), GCP, and all applicable regulatory requirements. Monitoring details describing strategy (e.g., risk-based initiatives in operations and quality such as Risk Management and Mitigation Strategies and Analytical Risk-Based Monitoring), methods, responsibilities and requirements, including handling of noncompliance issues and monitoring techniques (central, remote, or on-site monitoring) are provided in the Monitoring Plan.

The sponsor or designee is responsible for the data management of this study including quality checking of the data. The sponsor assumes accountability for actions delegated to other individuals (e.g., Contract Research Organizations).

Study monitors will perform ongoing source data verification to confirm that data entered into the CRF by authorized site personnel are accurate, complete, and verifiable from source documents; that the safety and rights of participants are being protected; and that the study is being conducted

in accordance with the currently approved protocol and any other study agreements, ICH GCP, and all applicable regulatory requirements. This review may occur at the study site or remotely. Any records supplied by the site for the purpose of remote monitoring and remote source document verification must comply with local legislation and the process approved by the local IRB, when required.

Records and documents, including signed ICFs, pertaining to the conduct of this study must be retained by the investigator for at least 5 years after the completion of the clinical trial, at least 2 years after the last approved marketing application and until there are no pending or contemplated marketing applications, or at least 2 years have elapsed since the formal discontinuation of clinical development of the study drug (whichever of the above requirements is the longest) unless local regulations or institutional policies require a longer retention period. No records may be destroyed during the retention period without the written approval of the sponsor. No records may be transferred to another location or party without written notification to the sponsor.

10.1.9 Source Documents

Source documents provide evidence for the existence of the participant and substantiate the integrity of the data collected. Source documents are filed at the investigator's site. Source documents specification per site will be agreed prior to first participant enrolled at the site. Data reported in the eCRFs must be consistent with the source documents or the discrepancies must be explained. The investigator may need to request previous medical records or transfer records, depending on the study. Also, current medical records must be available. Any records supplied by the site for the purpose of remote monitoring and remote source document verification must be de-identified using only the unique trial specific participant identifier. This process will be aligned with local ethics and privacy requirements.

Any investigators shall supply the sponsor, upon request, with any required background data from the study documentation or clinic records. This is particularly important when errors in data transcription are suspected. In case of special problems and/or governmental queries or requests for audit inspections, it is also necessary to have access to the complete study records, provided that participant confidentiality is protected.

Definition of what constitutes source data may include: participant hospital/clinic records, physician's and nurse's notes, appointment book, original laboratory reports, ECG, X-ray, pathology and special assessment reports, signed consent forms, consultant letters, and source worksheets.

The investigator must maintain adequate and accurate records to enable the conduct of the study to be fully documented and the study data to be subsequently verified. These documents should be classified into two different separate categories: (1) Investigator's Study File; and (2) Participant Clinical Source Documents.

The Investigator's Study File will contain the Protocol/Amendments, CRFs, IRB and governmental approval with correspondence, all versions of IRB approved informed consent

forms, staff curriculum vitae and authorization forms and other appropriate documents / correspondence, etc.

The investigator must keep these two categories of documents on file according to local clinical trial regulation. All study documents for a regulated trial require storage for at least 5 years after the completion of the clinical trial, at least 2 years after the last approved marketing application and until there are no pending or contemplated marketing applications, or at least 2 years have elapsed since the formal discontinuation of clinical development of the IMP (whichever of the above requirements is the longest). After that period of time the documents may be destroyed, participant to local regulations.

The investigator and the sponsor will maintain the records of disposition of the drug and the clinic records in accordance with ICH GCP and each applicable regulatory agency. Clinic records will be retained at the site until informed by the sponsor to destroy the documents. If the clinical study must be terminated for any reason, the investigator will return all study materials to the sponsor and provide a written statement as to why the termination has taken place and notify the IRB.

10.1.10 Study and Site Start and Closure

The study start date is the date on which the clinical study will be open for recruitment of patients.

The first act of recruitment is the first site open and will be the study start date.

The sponsor designee reserves the right to close the study site or terminate the study at any time for any reason at the sole discretion of the sponsor. Study sites will be closed upon study completion at 90 days. A study site is considered closed when all required documents and study supplies have been collected and a study-site closure visit has been performed.

The investigator may initiate study-site closure at any time, provided there is reasonable cause and sufficient notice is given in advance of the intended termination.

Reasons for the early closure of a study site by the sponsor or investigator may include but are not limited to:

- Failure of the investigator to comply with the protocol, the requirements of the IRB or local health authorities, the sponsor's procedures, or GCP guidelines
- Inadequate recruitment of participants by the investigator
- Discontinuation of further study intervention development

If the study is prematurely terminated or suspended, the sponsor shall promptly inform the investigators, the IRBs, the regulatory authorities, and any contract research organization(s) used in the study of the reason for termination or suspension, as specified by the applicable regulatory requirements. The Investigator shall promptly inform the participant and should assure appropriate participant therapy and/or follow-up.

10.1.11 Publication Policy

The results of this study may be published or presented at scientific meetings. If this is foreseen, the investigator agrees to submit all manuscripts or abstracts to the sponsor before submission. This allows the sponsor to protect proprietary information and to provide comments.

The sponsor will permit any and all academic publications arising from the trial data provided that no publication containing unblinded trial data precedes publication of the overall trial results in a peer-review journal, they are approved by the trial executive committee, and the publication authors notify the sponsor at least 30 days prior to submittal for publication with a copy of such proposed publication for the sponsor's review and comment. Employees or consultants of the sponsor will only be named as authors in any such publication if the parties agree that it is appropriate under the usual conventions used by academic institutions for naming authors in scientific publications. Upon request of the sponsor the publication or disclosure shall be delayed for up to 60 days in order to allow for the filing of a patent application.

The sponsor will comply with the requirements for publication of study results. In accordance with standard editorial and ethical practice, the sponsor will generally support publication of multicenter studies only in their entirety and not as individual site data. In this case, a coordinating investigator will be designated by mutual agreement.

A trial executive committee shall be formed and include at least the trial principal investigator and co-principal investigator, the statistical consultant, and representatives of the sponsor. The trial executive committee will be co-authors on all publications and presentations. The primary author list for the primary publication will consist of the executive committee and the site principal / qualified investigator at each of the sites. A formal publication policy will be presented and developed by the trial executive.

Authorship will be determined by mutual agreement and in line with International Committee of Medical Journal Editors authorship requirements.

10.1.12 Audits and Inspections

In accordance with the principles of ICH E6 Guideline for Good Clinical Practice, the study site may be inspected by regulatory authorities and/or audited by the sponsor or its designates. The investigator and relevant clinical support staff will be required to be actively involved in audits and inspections, including staff interviews, and to make all necessary documentation and data available upon request.

During the course of the study and/or after it has been completed, one or more investigator site audits may be undertaken by auditors from the sponsor or its delegates. The purpose of these audits is to determine whether or not the study is being/has been conducted and monitored in compliance with recognized ICH E6 Guideline for Good Clinical Practice, protocol and approved amendment requirements, applicable local SOPs, and local laws and regulations. It is the responsibility of the investigator and site staff to promptly address, by coordinating with the

sponsor, any deficiencies stemming out of regulatory inspections and sponsor or delegate audits, and to ensure that agreed-upon corrective and preventive actions are implemented as soon as possible.

An inspection by any regulatory authority may occur at any time during or after completion of the study. If an investigator is contacted by a regulatory authority for the purpose of conducting an inspection or to discuss any compliance issues, he/she is required to contact the sponsor immediately.

10.2 Appendix 3: Clinical Laboratory Tests and Imaging

10.2.1 Clinical Laboratory Tests

The tests detailed in [Table 10-1](#) will be performed as per local hospital laboratory.

Table 10-1: Protocol-Required Safety Assessments

Laboratory Tests	Parameters
Hematology	Platelet count Hemoglobin Hematocrit
Chemistry	Blood Urea Nitrogen Coagulation Panel (PTT and INR) Liver function test panel (ALT, AST and Bilirubin) Serum creatinine Serum glucose
Electrolytes	Sodium Potassium Chloride Bicarbonate Magnesium
Pregnancy testing	Highly sensitive (serum or urine) human chorionic gonadotropin (β -hCG) pregnancy test (as needed for women of childbearing potential)
Electrocardiogram	Frequent premature ventricular contractions or PVCs (> 10/min), ventricular tachycardia (VT), hypoxia, ischemia
CXR	Monitor fluid

10.2.2 Imaging

At baseline all participants will undergo NCCT and CTA (with mCTA preferred) imaging for assessment of inclusion into the trial. If mCTA is not standard of care at the imaging facility, single phase CTA (CTA) can be used to confirm intracranial occlusion eligibility. If CTA is not available, CTP may be used. To evaluate for the presence or absence of collaterals, mCTA, single phase CTA or CTP can be utilized. The immediate post-thrombectomy (within approximately 2 hours) and 48-h MRI will be used to assess perfusion imaging and infarct volume and will include a minimum of axial DWI, gradient-echo (GRE), FLAIR, T2, and 3D T1 weighted dataset). The 48-h MR is considered a standard of care imaging procedure. If any MRI cannot be obtained (due to subject compliance or limitations) a CT will be performed.

The baseline NCCT and CTA and all brain/neurovascular imaging conducted up to the Day 90 MR will be rendered anonymous and sent to the central core imaging lab. The core imaging lab staff will review the imaging as per an Imaging Charter in order to ensure adherence to the imaging guidelines and enrollment criteria for training purposes. The core imaging lab will confirm determination of baseline ASPECT scores, as well as reperfusion rates (TICI scores) and infarct growth from immediately after thrombectomy to 48h. In addition, overall injury to the

affected hemisphere will be compared between groups by comparing volume loss/gliosis between the 90-d and post-thrombectomy MRI.

For all interval times assessed from imaging, the time zero will be the first slice of the NCCT scan. Imaging date and time will be collected in the CRF.

Notes:

The use of a dynamic CTA or multiphase CTA data acquisition protocol is preferred. Baseline NCCT and CTA may be completed at a hospital affiliated with the trial site.

10.3 Appendix 4: Adverse Events: Definitions and Procedures for Recording, Evaluating, Follow-up, and Reporting

AE Definition

An AE is any untoward medical occurrence in a patient or clinical investigation participant administered a pharmaceutical product and which does not necessarily have to have a causal relationship with this treatment.
 
An AE can therefore be any unfavorable and unintended sign (including an abnormal laboratory finding, for example), symptom or disease temporally associated with the use of a medicinal product, whether or not considered related to the medicinal product.


Adverse Drug Reaction (ADR)
 
In the pre-approval clinical experience with a new medicinal product or its new usages, particularly as the therapeutic dose(s) may not be established: all noxious and unintended responses to a medicinal product related to any dose should be considered adverse drug reactions. The phrase "responses to a medicinal product" means that a causal relationship between a medicinal product and an adverse event is at least a reasonable possibility, i.e., the relationship cannot be ruled out.

Unexpected Adverse Drug Reaction
 
An adverse reaction, the nature or severity of which is not consistent with the applicable product information (e.g., Investigator's Brochure for an unapproved investigational medicinal product).

Events Meeting the AE Definition

• A new illness• The worsening of a concomitant illness• Any abnormal laboratory test results (hematology, clinical chemistry, or urinalysis) or other safety assessments (e.g., ECG, radiological scans, vital signs measurements), including those that worsen from baseline, considered clinically significant in the medical and scientific judgment of the investigator (i.e., not related to progression of underlying disease).• Exacerbation of a chronic or intermittent pre-existing condition including either an increase in frequency and/or intensity of the condition.• New conditions detected or diagnosed after study intervention administration even though it may have been present before the start of the study.• Signs, symptoms, or the clinical sequelae of a suspected drug-drug interaction.• Signs, symptoms, or the clinical sequelae of a suspected overdose of either study intervention or a concomitant medication. Overdose per se will not be reported as an AE/SAE unless it is an intentional overdose taken with possible suicidal/self-harming intent. Such overdoses should be reported regardless of sequelae.
Events NOT Meeting the AE Definition

- Any clinically significant abnormal laboratory findings or other abnormal safety assessments which are associated with the underlying disease.
- The disease/disorder being studied or expected progression, signs, or symptoms of the disease/disorder being studied, unless more severe than expected for the participant's condition.
- Medical or surgical procedure (e.g., endoscopy, appendectomy): the condition that leads to the procedure is the AE.
- Situations in which an untoward medical occurrence did not occur (social and/or convenience admission to a hospital).
- Anticipated day-to-day fluctuations of pre-existing disease(s) or condition(s) present or detected at the start of the study that do not worsen.
- Pre-existing medical conditions are not to be reported as AEs. However, if a pre-existing condition worsens in frequency or intensity, or if in the assessment of the treating physician there is a change in its clinical significance, this change should be reported as an AE (exacerbation). This applies equally to recurring episodes of pre-existing conditions (e.g., asthma) if the frequency or intensity increases post-randomization.

10.3.1 Definition of SAE

If an event is not an AE per definition above, then it cannot be an SAE even if serious conditions are met (e.g., hospitalization for signs/symptoms of the disease under study, death due to progression of disease).

A SAE is defined as any untoward medical occurrence that, at any dose:

a. Results in death

All deaths occurring during the follow up to Day 90 will be reported as an SAE. When reporting a death, the event or condition that caused or contributed to the fatal outcome should be reported as a single medical concept.

b. Is life-threatening

The term 'life-threatening' in the definition of 'serious' refers to an event in which the participant was at risk of death at the time of the event. It does not refer to an event, which hypothetically might have caused death, if it were more severe.

c. Requires inpatient hospitalization or prolongation of existing hospitalization

- In general, hospitalization signifies that the participant has been detained (usually involving at least an overnight stay) at the hospital or emergency ward for observation and/or treatment that would not have been appropriate in the physician's office or outpatient setting. Complications that occur during hospitalization are AEs. If a complication prolongs hospitalization or fulfills any other serious criteria, the event is

	
serious. When in doubt as to whether “hospitalization” occurred or was necessary, the AE should be considered serious.
 
• Hospitalization for elective treatment of a pre-existing condition that did not worsen from baseline is not considered an AE.
d.	
Results in persistent disability/incapacity
 
• The term disability means a substantial disruption of a person’s ability to conduct normal life functions.• This definition is not intended to include experiences of relatively minor medical significance such as uncomplicated headache, nausea, vomiting, diarrhea, influenza, and accidental trauma (e.g., sprained ankle) which may interfere with or prevent everyday life functions but do not constitute a substantial disruption.
e.	
Results in a congenital anomaly/birth defect

f.	
Other situations: a SAE can also be an important medical event that may not result in death, be life-threatening, or require hospitalization, but may jeopardize the participant and may require medical or surgical intervention to prevent one of the outcomes listed in this definition:
 
• Medical or scientific judgment should be exercised in deciding whether SAE reporting is appropriate in other situations such as important medical events that may not be immediately life-threatening or result in death or hospitalization but may jeopardize the participant or may require medical or surgical intervention to prevent one of the other outcomes listed in the above definition. These events should usually be considered serious.• Examples of such events include invasive or malignant cancers, intensive treatment in an emergency room or at home for allergic bronchospasm, blood dyscrasias or convulsions that do not result in hospitalization, or development of drug dependency or drug abuse.

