8.2.1 Time Period and Frequency for Collecting AE and SAE Information

All SAEs will be collected from the start of study drug administration until Day 90, in addition SAE assessed as related to study drug or that have a fatal outcome will be collected to Day 90, see [Table 1-1: Schedule of Activities](#).

All AEs will be collected from the start of study drug administration through Day 90 at the time points specified in [Table 1-1: Schedule of Activities](#).

Medical occurrences that begin before the start of study intervention but after obtaining informed consent will be recorded in the Past Medical and Surgical History section of the electronic case report form (CRF), not in the AE section.

All SAEs will be recorded and reported to the sponsor or designee within 24 hours of knowledge of the event, as indicated in [Appendix 4: Adverse Events: Definitions and Procedures for Recording, Evaluating, Follow-up, and Reporting](#). The investigator will submit any updated SAE data to the sponsor within 24 hours of it being available.

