1 INTRODUCTION

The purpose of this statistical analysis plan (SAP) is to provide a description of the statistical methods to be implemented for the analysis of data from the study with protocol number 06.5.1.H1 dated 09 May 2022 (version 2.4). The SAP will be finalized prior to database lock. Any future addendum to the SAP (if applicable) will be referenced in the Clinical Study Report (CSR).

The SAP will be considered as the governing document and in case of any differences between this SAP and the study protocol, the SAP will supersede the protocol.

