3.4 Safety and Efficacy Assessments

The primary safety analysis will be conducted in the Safety Population. The secondary efficacy analysis will be conducted in the ITT and PP Populations.

3.4.1 *Primary Safety Endpoints*

Frequencies and severities of SAEs

The proportion of participants with SAEs through Day 90 between the three treatment groups (RNS60 0.5 mL/kg/h, RNS60 1.0 mL/kg/h, and placebo 1.0 mL/kg/h)

In addition, the frequency and severity categories will be summarized with counts and percentages of SAEs by treatment and site and in total. See Appendix C for definition of SAE.

90-day Mortality

The proportion of participants alive at Day 90 between the three treatment groups (RNS60 0.5 mL/kg/h, RNS60 1.0 mL/kg/h, and placebo 1.0 mL/kg/h).

3.4.2 *Secondary Efficacy Endpoints*

All outcomes will be assessed in the following hierarchical order (to control of the overall Type I error rate). As it is hypothesized that higher dosage will result in less disability, subjects receiving placebo 1.0 mL/kg/h will first be compared to RNS60 1.0 mL/kg/h and then, as a lower ranking secondary endpoint, combined RNS60 doses (1.0 mL/kg/h and 0.5 mL/kg/h) compared to placebo, and finally RNS60 0.5 mL/kg/h compared to placebo. Specifically, efficacy of each of the 5 key endpoints will be assessed between high-dose RNS60 compared to placebo, followed by the same endpoints between combined RNS60 doses (1.0 mL/kg/h and 0.5 mL/kg/h) compared to placebo, finally followed by the same 5 endpoints between RNS60 low dose (0.5 mL/kg/h) compared to placebo:

1. Disability based on mRS score, high-dose vs placebo
2. Infarct progression/regression, high-dose vs placebo
3. NIHSS score, high-dose vs placebo
4. Worsening of stroke high-dose vs placebo
5. BI, high-dose vs placebo
6. Disability based on mRS score, combined-dose vs placebo
7. Infarct progression/regression, combined-dose vs placebo
8. NIHSS score, combined-dose vs placebo
9. Worsening of stroke, combined-dose vs placebo

10. BI, combined-dose vs placebo
11. Disability based on mRS score, low-dose vs placebo
12. Infarct progression/regression, low-dose vs placebo.
13. NIHSS score, low-dose vs placebo
14. Worsening of stroke, low-dose vs placebo
15. BI, low-dose vs placebo

If a comparison listed above is determined to be not statistically significant, then the remaining comparisons in the hierarchy will be tested in any case and interpreted in an exploratory manner.

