3.5.1 Adverse Events (AEs)

An AE is defined as any untoward medical occurrence in a subject or clinical investigation participant administered a pharmaceutical product and which does not necessarily have to have a causal relationship with this treatment.

An AE can therefore be any unfavorable and unintended sign (including an abnormal laboratory finding, for example), symptom or disease temporally associated with the use of a medicinal product, whether or not considered related to the medicinal product. AEs will be captured from the start of study drug infusion through study completion (Day 90). All AEs will be coded to system organ class and preferred term using MedDRA version 24.0. A medical review of the coding reports will be performed prior to database lock. Treatment-emergent adverse events (TEAEs) are defined as AEs that start after the study drug infusion.

The investigator will grade the intensity of the AE as mild, moderate, or severe.

The relationship of an AE to study drug will be assessed as related, possibly related, or unrelated.

An overview of AEs will be provided including counts and percentages of subjects (and event counts) with the following:

- Any TEAEs (overall and by maximum severity)
- Any study drug related TEAEs (overall and by maximum severity)
- Any SAEs
- Any treatment-emergent serious AEs (TESAEs)
- Any study drug related TESAEs
- Any TEAEs leading to discontinuation of study drug infusion
- Any AEs leading to death
- TEAE occurrence by Month (Day 0-Day 7, Day 8 – Day 14, Day 15 – Day 21, Day 22 – Day 30, Day 31-Day 60, and Day 61-Day 90)

Counts and percentages of subjects (and event counts) will also be presented by system organ class and preferred term for each of the categories in the overview. If more than one event occurs with the same preferred term for the same subject, the subject will be counted only once for that preferred term using the most severe occurrence for the summary by severity. The number of events will be presented for overall category of TEAE and for each system organ class and preferred term. The number of events will not be presented for each category of maximum severity. AE listings will include the following information:

- Subject ID
- Adverse event term
- Adverse event preferred term
- System Organ Class
- Start date
- Outcome
- End date
- Relationship to study drug
- Action taken with study drug

- Severity
- SAE Criteria

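### Protocol 10.3.1 both excludes deaths from disease progression from SAEs and requires every death to Day 90 to be reported as one, so recorded SAE counts could omit stroke deaths

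*Protocol*

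**What the plan says.** Protocol 10.3 (Appendix 4) lists events that do not meet the AE definition. The list includes "expected progression, signs, or symptoms of the disease/disorder being studied, unless more severe than expected" for that participant. Protocol 10.3.1 builds on it: "If an event is not an AE per definition above, then it cannot be an SAE even if serious conditions are met", with two examples, "hospitalization for signs/symptoms of the disease under study, death due to progression of disease". Criterion (a) of the same section says: "All deaths occurring during the follow up to Day 90 will be reported as an SAE".

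SAP Appendix C carries the criterion (a) sentence in the same words and does not carry the exclusion. SAP 1 adds that "in case of any differences between this SAP and the study protocol, the SAP will supersede the protocol".

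On the analysis side, SAP 3.4.1 gives as a primary safety endpoint "The proportion of participants with SAEs through Day 90 between the three treatment groups". SAP 3.5.1 includes the overview row "Any AEs leading to death". Protocol 9.3.2 summarizes fatal SAEs, and Protocol 9.3.3 plans Fisher's exact tests on SAEs and on SAEs resulting in death. Mortality status is collected separately at every visit (Protocol 8.1.7), and 90-day mortality is the other primary safety endpoint.

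**The concern.** In this population, death from progression of the index stroke is a foreseeable event, and the protocol gives two opposite instructions for classifying it. The choice turns partly on whether the investigator judges the progression to be within what was expected, so sites could differ.

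The summaries at stake are those that count recorded SAEs or AEs: the SAE proportion, the fatal-SAE comparison and the table of AEs leading to death. If a death is not entered as an SAE, these could be too low and could disagree with the mortality count in the same report. Worsening of stroke may also be touched, because SAP 3.4.2 (item 4) identifies cases partly from adverse event status in the CRF. That exposure is only possible, not certain: SAP 2.1.3 treats death as a worsening, and SAP 3.1.7 assigns the worst NIHSS score after death, so a death might be picked up by another route.

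**Working it through.** The plan gives no figure to reproduce. The check is a comparison of text, followed by a bound on scale.

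**1. Do the two rules apply to the same event?** Take a death from expected progression of the index stroke.
- Under Protocol 10.3, expected progression is not an AE. Under the opening of 10.3.1, what is not an AE cannot be an SAE, whatever serious criterion it meets. Death is one of those criteria, and a progression death is one of the named examples. Result: not an SAE.
- Under criterion (a), every death to Day 90 is reported as an SAE. Result: an SAE.

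The conflict is direct because the excluded example is itself a death.

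**2. Does other protocol text decide between them?** Protocol 8.2.1 says that "SAE assessed as related to study drug or that have a fatal outcome will be collected to Day 90". This takes the event to be an SAE already, so it does not settle whether it is one. No other protocol sentence ranks the two rules.

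**3. Does the SAP decide?** Appendix C and the precedence clause settle the definition for the analysis. They cannot supply a record that a site never made, because SAP 3.4.1 and 3.5.1 count recorded events. The SAP states no match of deaths to SAE records. One may exist in the Data Management Plan or Safety Management Plan named in SAP 2.2.2, which are not available here, or within the general data checks of Protocol 10.1.8.

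**4. Scale.** Inputs:
- N = 100 (Protocol 4.1; SAP 2.2.4), allocated 1:1:1, so about 33 per arm. All are assumed to be treated and so in the Safety Population.
- 10% death from stroke (Protocol 9.1; SAP 2.2.4). Both documents call this an attrition factor. Using it as the stroke-death rate to Day 90 is an assumption.

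Exposed deaths: D = 100 × 0.10 = 10 in the trial, or 10/3 = 3.3 per arm.

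Chance of at least one in an arm of 33: 1 − 0.90^33 = 0.969. At that rate the ambiguous case would very probably arise.

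Understatement of the SAE proportion = D × r × g / N, where r is the share of stroke deaths withheld as expected progression and g is the share of those participants with no other recorded SAE.
- r = 0 or g = 0: 0 percentage points.
- r = g = 1: 10 × 1 × 1 / 100 = 10 percentage points. This is the upper bound.

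The documents give neither r nor g. Moreover, r should be below 1 wherever a stroke death is judged more severe than expected, since such a death remains an AE under Protocol 10.3.

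**The case against.** The strongest reply is that the all-deaths rule plainly governs. It is mandatory and universal, while the exclusion is general and conditional. Criterion (a) also says how to record the cause of a death, which fits a rule that covers all of them. Protocol 8.2.3 treats a death as a kind of SAE. Protocol 10.3.2 calls an event serious once it meets any one of the listed outcomes. SAP 3.4.2 expects fatal stroke worsening to appear in the adverse event data. SAP Appendix C and the precedence clause point the same way. This stands as evidence of intent. It does not remove the conflict: none of these texts states precedence, and a site could reasonably treat the named example as the narrower rule.

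The second reply is that little can be lost. Deaths are ascertained independently at every visit, vital status is sought even for participants who cannot be reached (Protocol 7.3), and the DSMB sees unblinded safety data (SAP 4). A shortfall would show as a mismatch and could be corrected before lock, perhaps under a plan not seen here. This also stands, and it limits the weight of the point. It is also the reason why an explicit match is worth stating.

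A reader might infer that trial mortality is undercounted, or that an arm could show no fatal SAEs against several recorded deaths. The first is not supported, because mortality has its own record. The second would require every death in that arm to be a stroke death withheld as expected progression; deaths from other causes are not covered by the exclusion.

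**Conclusion.** The contradiction in Protocol 10.3.1 is certain on the text. Its effect is conditional: it arises only where a site follows the exclusion and the participant has no other recorded SAE. If the 10% attrition factor is assumed to be the stroke-death rate to Day 90, about 10 of 100 participants are exposed, and the SAE proportion is understated by between 0 and at most 10 percentage points. Any single value inside that range would rest on invented shares.

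A reader might also infer a bias between arms. The documents show none: both rules apply alike to all three arms, and nothing indicates that sites would apply them differently by treatment. The point should be fixed because it concerns the recorded content of a primary safety endpoint and the remedy is small. It does not call the 90-day mortality endpoint into question.

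**What to change.** 1. Reconcile Protocol 10.3 and 10.3.1 with SAP Appendix C. State that neither the rule tying SAEs to the AE definition nor the carve-out for expected progression applies to deaths to Day 90, and take the progression-death example out of the opening sentence of 10.3.1. Deleting the example alone would leave the general rule in force.
2. Before database lock, match every death to Day 90 in the mortality record of a Safety Population participant to an SAE record with a fatal outcome, and query mismatches. State this in SAP 3.4.1, or cross-reference the Data Management Plan or Safety Management Plan if one of them already requires it.

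Cost: a short protocol clarification (with IRB approval if made as an amendment), one or two sentences in the SAP, and one reconciliation listing. The downside is a few more SAE reports and a slightly higher SAE proportion. If follow-up has already ended, the second step alone can still recover the counts.
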